Appendix O. Household level end-line survey (to be completed mid 2017)

	Barcode (from last visit)	Name	House hold head (check if yes)	Index case (check if yes)	Gender	Date of birth	Consent obtained for today's blood collection (yes/no)	Participated in intervention (yes/no)	Have you been diagnosed with malaria since you first participated in the study intervention? Yes/No If yes list date or dates YY/MM/DD	Have you had fever in the past 2 weeks? (yes/no)	Have you take antimalarial medication in the past 2 months? Yes/No If yes, what treatment was prescribed? Check all that apply  AL (Coartem)  Single dose primaquine  Oral Quinine  IV Quinine  IM Quinine  IV Artesunate  IM Artesunate  Chloroquine  SP/Fansidar  Other (specify _____)  Unknown Was full treatment course completed?  Yes  No  Don't know On what day was the last treatment started? YY/MM/DD	Have you spent at least one night outside of this village in the past 8 weeks? If yes, complete travel information below.	DBS collected today? (yes/no)	Notes
1.														Edit
2.														Edit
Etc.														Add Individual

Note: Shaded areas will be automatically generated from the all previous visits to this household. For each individual, confirm this data. If

Note: Add a new line for individuals

Travel information

Within Swaziland			Outside of Swaziland		
Village / town/ District where you have spent the night(s)	Duration of stay		Country/Province/Town where you have spent the night(s)	Duration of stay	
	First Night DD/MM/YY	Last Night DD/MM/YY		First Night DD/MM/YY	Last Night DD/MM/YY

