1. To determine the feasibility of obtaining at least 80% coverage of TPE, and compare coverage to that attained using RACD. Coverage will be defined as receipt of and adherence to the first dose of DP within initial visits by the study team in the TPE arm or receipt of a blood test in the RACD arm. Our **hypothesis** is that the coverage attainable for TPE will be at least 80%. We also hypothesize that coverage for TPE will be equivalent to RACD but we will not be powered to prove this hypothesis.
2. To measure adherence to a 3-day regimen of DP administered by modified DOT delivery system in the TPE arm. We hypothesize adherence will be 80%.
3. To compare potential serious adverse events associated with TPE and RACD. We will test the hypothesis that the risk of serious adverse events will not be higher in individuals receiving TPE versus RACD.
4. To compare the acceptability of TPE versus RACD as assessed by refusal rates and a qualitative assessment. We hypothesize that TPE will not be inferior to RACD in terms of acceptability and may be more desired.
5. To compare the costs of TPE versus RACD. We will test the hypothesis that the costs per event will not be higher for individuals receiving TPE compared to RACD and may be cost-saving.

4 Study design & methods

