8.1 Overview

The safety risks associated with participation in this trial are expected to be minimal. AL, the current standard of care in Swaziland, is generally well tolerated and, at least by passive monitoring, has been associated with only minimal adverse effects in Swaziland. DP is one of the ACT regimens recommended by the WHO[23], and is recommended as a second line treatment for uncomplicated malaria in many countries[24]. The safety and tolerability of DP have been closely evaluated in clinical trials evaluating DP for treatment and prevention of malaria, and DP has been shown to have an excellent safety profile[10, 11, 25, 26]. In the TPE arm, prior to drug administration, subjects will be asked about known allergy, past adverse reactions felt to be associated with treatment, and other contraindications (see Table 3) and will be excluded from taking drug if such a history is reported.

Adverse event monitoring of SAEs potentially related to AL or DP will occur passively. Subjects will be instructed to seek care at their local health facility if they experience any serious adverse reactions that may be related to AL or DP. Health facility physicians will determine if a participant should continue or stop treatment due to safety concerns. Health facility staff will be asked to notify study staff of all adverse events. For any adverse events that are reported in either arm, we will attempt to assess causality by collecting additional data on the relationship between the drug and the event. This information will be reported and reviewed by the Pharmacovigilance and Adverse Drug Reactions Committee (the Data Safety & Monitoring Board for this study).

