8.2 Definitions

- Serious adverse event (SAE): An experience that results in (1) death during the study period; (2) life-threatening experience (one that puts a participant at immediate risk of death at the time of the event); (3) inpatient hospitalization during the study period; (4) persistent or significant disability or incapacity, (4) specific medical or surgical intervention to prevent one of the other serious outcomes listed above.
- Suspected Unexpected Serious Adverse Reactions (SUSAR): An adverse drug reaction that is suspected of having a causal relationship to the trial medication and is unexpected

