Appendix P. End-line Individual questionnaire

Patient Details

1. Patient Name _____
2. Date of birth |__|_|/|__|_|/|__|_|
date month year
3. Gender Male Female
4. Inkhundla _____
5. Locality _____
6. Study ID: _____
7. Household ID: _____
8. Consent obtained: Yes No
9. Ask: Did you participate in the initial study intervention?
 TPE Arm
 RACD Arm
 Did not participate

If yes, ask: Have you taken malaria medication as a part of this study? Yes No

If yes, ask: What malaria medication did you take?

- Dihydroartemisinin-piperaquine (Eurartesim)
- Artemether-lumefantrine (Coartem)
- Other (specify _____)
- Unknown

If yes, ask: Did you experience any adverse events that you think may have been related to the malaria medication? Yes No

If yes, ask: Please describe these adverse events.

10. Ask: Have you been diagnosed with malaria in the past 12 months? Yes No

If yes, ask when,

- 6 months to a year ago
- < 6 months ago
- Within the last month
- Within the last 2 weeks
- Don't know

If yes ask, have you had fever in the last 2 weeks? Yes No Don't know

If yes ask, have you been diagnosed with malaria in the last 2 weeks? Yes No Don't know

If diagnosed in the last 2 weeks:

Was the diagnosis confirmed by a test? Yes No Don't know

What treatment was prescribed? *Check all that apply*

- Artemether-lumefantrine
- Single dose primaquine
- Oral Quinine
- IV Quinine
- IM Quinine
- Chloroquine
- SP/Fansidar
- Other (specify _____)
- Unknown

Was full treatment course completed? Yes No Don't know

13. *Comments or any other information that is relevant?*

14. RDT result: positive negative not done

If positive, patient referred to local health facility Yes No

If no, why?

DBS collected Yes No Not Done

If DBS not done, why? Patient refused Other _____

Thank you for our participation in this study.

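### The end-line forms have no coded item for death, departure or hospital admission, and their only adverse-event question would reach about 0.5% of RACD residents against 80-100% of TPE residents, so the SAE comparison has no symmetric back-up check

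*Combined protocol and SAP*

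**What the plan says.** Section 8.2 defines an SAE without any relatedness condition. The first criterion reads "An experience that results in (1) death during the study period" and the third is "inpatient hospitalization during the study period".

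On detection, section 8.1 says "Adverse event monitoring of SAEs potentially related to AL or DP will occur passively". Participants are told to report events that may be due to AL or DP. Facility staff are asked to pass on all adverse events, and sections 8.3 and 8.4 add a 24-hour study nurse line and a report form for each serious illness identified.

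Section 3 (feasibility aim 3) states: "We will test the hypothesis that the risk of serious adverse events will not be higher in individuals receiving TPE versus RACD". Table 6 narrows the outcome to SAEs at least possibly related to DP or AL, over all enrolled. Section 14.4 expects few or none.

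At end-line, the Appendix O roster is pre-filled: "Shaded areas will be automatically generated from the all previous visits to this household. For each individual, confirm this data". The instruction breaks off just after that, at the first word of a conditional sentence. The columns cover identity, consent, participation, malaria, fever, antimalarials, travel, DBS and notes. Appendix P item 9 asks "Did you experience any adverse events that you think may have been related to the malaria medication", after a yes to taking part and a yes to having taken study malaria medication.

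**The concern.** Passive reporting can miss a death at home, or an event that nobody connects with the study. The end-line visit could catch some of these, because it returns to enrolled households in both arms with a list of who was there before. As printed, the forms do not ask what became of the people on that list. The safety question they do contain is conditioned on drug intake, which is nearly the same as conditioning on arm.

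At stake is how the final SAE comparison can be read. Causality is assigned after study-physician review (section 8.6, Appendix S), and an event that is never ascertained never reaches review. Active prompting is denser in TPE, while absence of a vital-status check can hide deaths in either arm. A small difference between arms, or none, would then be hard to interpret.

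**Working it through.** **1. Coded fields across the forms**

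| Form | Present/absent or reason | Died | Moved | Admitted |
|---|---|---|---|---|
| Appendix D (unsuccessful investigation) | yes | yes | yes | place of investigation only |
| Appendices H and J (intervention rosters) | yes | no | no | no |
| Appendix O (end-line roster) | no, free-text notes | no | no | no |

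The study's other forms therefore code absence, and one codes death and moving. The end-line roster codes none of them.

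**2. Active contacts with non-index residents after the intervention visits**

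| Contact | TPE | RACD |
|---|---|---|
| Pill count at 7-10 days, with side-effect question (Table 3, section 7.5, Appendix K) | first Target Area per locality per season; staff may return | none |
| 6-9 month visit (Table 3) | excluded | secondary cases and some controls |
| End-line survey (section 9.3) | all Target Area residents | all Target Area residents |

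Section 14.1 expects 22 TPE localities with an index case. Over two seasons the pill count covers at most 22 x 2 = 44 of the 66 expected TPE events. For non-index residents, only the end-line visit is made on the same terms in both arms.

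**3. Reach of the Appendix P adverse-event question**

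Reproducing the plan's figures first:
- All residents (section 14.1): 200 index cases x 30 = 6,000; less 10% repeats, 6,000 x 0.9 = 5,400. Matches.
- TPE (section 14.3): 66 x 30 x 0.9 = 1,782. Matches.

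Then:
- RACD by difference: 200 - 66 = 134 index cases; 134 x 30 x 0.9 = 3,618.
- Only RDT-positives are treated in RACD. Section 1.3 gives 42 of 8,355 = 0.503%. Expected treated: 3,618 x 42/8,355 = 18.2, about 18. With equal arms of 2,700 it would be 13.6, about 14.
- TPE: from 0.80 x 1,782 = 1,426 (the 80% coverage goal) to 1,782 (all treated, as section 14.3 words it).

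Share eligible for the question: 18/3,618 = 0.5% in RACD against 80-100% in TPE. This assumes that everyone is seen at end-line and that RACD residents regard AL from the clinic as study medication. If they do not, the RACD figure is lower.

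**4. Number of events**

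The documents give no death or admission rate. Assuming 2-15 deaths per 1,000 person-years and 0.5-1.5 years of mean follow-up, total deaths among 5,400 people run from 5,400 x 0.002 x 0.5 = 5.4 to 5,400 x 0.015 x 1.5 = 121.5. These are all deaths. The share missed by passive reporting, and the share related to drug, cannot be derived.

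**The case against.** The strongest reply is that end-line is not the SAE instrument. Passive reporting covers both arms, facilities are asked for all adverse events whatever their cause, and admissions happen in facilities. Section 9.3 gives serology as the survey's main purpose, section 2 says that safety is not the primary aim, and the outcome is related SAEs. This stands, and it limits the point to a missed back-up. It does not cover a death at home or an admission that a facility does not connect with a participant.

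A reader might infer that deaths and admissions go unrecorded at end-line. The documents do not support that. Appendix O has a notes column, Appendix P has a comments item, and the cut-off instruction may have held a rule for people no longer present. What can be said is that no printed field codes or prompts for status or admission.

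A reader might also infer that end-line is the only contact made alike for everyone. Index cases of both arms also have the 6-9 month visit, whose questionnaire (Appendix M) is not in the text available. The statement holds only for non-index residents, who are the people offered the interventions.

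Finally, someone who died or moved falls outside the end-line population (a night in the Target Area in the past 5 weeks), so is not a non-responder. Reporting what became of listed people is useful as a disposition table, not as a response rate.

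**Conclusion.** The concern holds in limited form. The end-line forms lack any structured item on vital status, residence or admission. Their only adverse-event question is gated so that it reaches about 18 RACD residents against about 1,426-1,782 in TPE. The other active contacts with non-index residents are also unequal, so the planned SAE comparison has no symmetric check behind passive reporting.

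The reach figures rest on the plan's own counts, its 2012-2014 RDT positivity and full end-line participation. The contrast does not depend on their exact values.

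It would be tempting to add that the stopping guidelines are compromised. They are not affected: a survey in mid 2017 comes too late to inform stopping, and section 16.3 uses causally associated SAEs. Nor can any number of missed events be stated. The change is worth making because the visit is already planned, but the trial's main safety route does not fail without it.

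**What to change.** - **Appendix O:** add a coded status for every pre-listed person in both arms (present, absent, refused, moved, died with date), answered by the household head.
- **End-line interview:** ask every respondent in both arms, in the same words and regardless of drug intake, about any overnight hospital admission since the intervention date (dates, reason). A parent or guardian answers for children. Each adult answers for himself or herself, so the head is not asked for other adults' medical details.
- **Appendix P:** ask the adverse-event item without the drug-intake gate.
- **Section 14.4:** report all-cause deaths and admissions by arm as a descriptive supplement to the related-SAE outcome. Show events within 2 months of the intervention separately (the interval that section 7.3 already uses for piperaquine) and send those for Appendix S completion and causality review. Report by arm how many listed people had died, moved, were absent or refused.

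The cost is recall error over up to about 20 months in an open-label trial, some additional Appendix S forms, and a small amendment to the questionnaire and consent text. Admissions of people who are absent, have moved or have died would still be missed.

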Appendix P. End-line Individual questionnaire

Patient Details

1. Patient Name _____
2. Date of birth |__|_|/|__|_|/|__|_|
date month year
3. Gender Male Female
4. Inkhundla _____
5. Locality _____
6. Study ID: _____
7. Household ID: _____
8. Consent obtained: Yes No
9. Ask: Did you participate in the initial study intervention?
 TPE Arm
 RACD Arm
 Did not participate

If yes, ask: Have you taken malaria medication as a part of this study? Yes No

If yes, ask: What malaria medication did you take?

- Dihydroartemisinin-piperaquine (Eurartesim)
- Artemether-lumefantrine (Coartem)
- Other (specify _____)
- Unknown

If yes, ask: Did you experience any adverse events that you think may have been related to the malaria medication? Yes No

If yes, ask: Please describe these adverse events.

10. Ask: Have you been diagnosed with malaria in the past 12 months? Yes No

If yes, ask when,

- 6 months to a year ago
- < 6 months ago
- Within the last month
- Within the last 2 weeks
- Don't know

If yes ask, have you had fever in the last 2 weeks? Yes No Don't know

If yes ask, have you been diagnosed with malaria in the last 2 weeks? Yes No Don't know

If diagnosed in the last 2 weeks:

Was the diagnosis confirmed by a test? Yes No Don't know

What treatment was prescribed? *Check all that apply*

- Artemether-lumefantrine
- Single dose primaquine
- Oral Quinine
- IV Quinine
- IM Quinine
- Chloroquine
- SP/Fansidar
- Other (specify _____)
- Unknown

Was full treatment course completed? Yes No Don't know

13. *Comments or any other information that is relevant?*

14. RDT result: positive negative not done

If positive, patient referred to local health facility Yes No

If no, why?

DBS collected Yes No Not Done

If DBS not done, why? Patient refused Other _____

Thank you for our participation in this study.

Appendix Q. DP weight-based dosing guidelines

Body weight (kg)	Daily dose (mg)		Tablet strength and number of tablets per dose
	PQP	DHA	
5 to <7	80	10	½ x 160mg / 20mg tablet
7 to <13	160	20	1 x 160mg / 20mg tablet
13 to <24	320	40	1 x 320mg / 40mg tablet
24 to <36	640	80	2 x 320mg / 40mg tablets
36 to <75	960	120	3 x 320mg / 40mg tablets
75 to 100	1,280	160	4 x 320mg / 40mg tablets
>100	There are no data on which to base a dose recommendation in patients weighing >100kg.		

Appendix R. Modified DOT dosing schedule

Day 1 DOT only arm

	Day 1	Day 2	Day 3	Day 4	Day 5
Present all 3 days	Rx 1 (DOT)	Rx 2 (self-admin)	Rx 3 (self-admin)		
Absent day 1		Rx 1 (DOT)	Rx 2 (self-admin)	Rx 3 (self-admin)	
Absent days 1 & 2			Rx 1 (DOT)	Rx 2 (self-admin)	Rx 3 (self-admin)

If needed to improve coverage, study staff will visit neighborhoods on Days 2 and 3. On these days, they may document that the dose that day was taken, remind subjects to take their medication, or directly observe ingestion.

Appendix S. Serious adverse event report form

To be completed by Study Physician

Adverse Drug Reactions (ADR) Report Form

Report can be returned to Central Medical Stores by fax [name] or [name]

Email [contact] or [contact] or

Post to: Adverse Drug Reaction, Central Medical Stores, [name]

For Further inquiries, please contact the Pharmacist (Pharmacovigilance) at Central Medical Stores at [name] or [name]

Section (A): Patient Information

Patient initials or ref. no: _____ Sex M F Pregnant? No Yes Unknown

Weight (if known): _____ kg Date of birth (dd/ mm/ yyyy) / / or age (at last birthday): _____

Section (B): Medication History

All Drug Therapies/ Vaccines Prior to ADR (Please use trade names and circle the suspected drug)	Batch number	Daily Dosage	Route	Date Begun	Date Stopped	Indication for Use

Allergies or other relevant history (including medical history, liver/ kidney problems, smoking, alcohol use etc)

Section (C): About the Adverse Drug Reaction

Date of onset of ADR (dd/ mm/ yyyy) / /

Description of event: _____

Category of ADR (please tick)

- Suspect minor/ major reaction from a drug (eg allergic reaction)
- Adverse Event (eg congenital defects)
- Product Use Error (eg use of antibiotic instead of NSAID)

Severity (can tick more than one if appropriate):

- Life threatening
- Hospitalized (dd/ mm/ yyyy) / /
- Hospitalization NOT required

Relevant Laboratory result: _____

Section (D): Treatment & Outcome

Treatment of ADR: No Yes. Details (including dosage, frequency, route, duration) -----

Outcome:

- Recovered on: (dd/mm/yyyy) / /
 - Not yet recovered
 - Unknown
 - Died on: (dd/mm/yyyy) / /
 - Persistent disability
 - Birth defect
 - Medically significant events
- Details: _____

Section (E): Reporter Details

Name: _____ Sector of service: Private Public
Occupation: Doctor Dentist Pharmacist Nurse Others _____
Correspondence Address: _____
Tel. no.: _____ Fax. no.: _____ Email: _____
Also report to: Manufacturer Distributor/Importer Others _____ Date of this report: _____

FOR OFFICIAL USE ONLY

Report to: Manufacturer Distributor/Importer Other _____

Reported by: _____ Capacity _____

Instructions/ Notes

1. ADR can be briefly described as a noxious and unintended response to a drug or vaccine when the normal dose is used.
2. This report form is used for voluntary reporting of all suspected ADR.
3. There is no need to put down the full name of the patient.
4. Please provide information to every section. Information of individual reporter will be treated with strict confidence.
5. Please use another page for additional information if necessary.
6. Where date is required write in this format DDMMYYYY

“Completion of this form is not an admission of guilt or negligence”

Additional questions (also completed by study physician):

20) Maximum severity (See WHO Grading) |_|_|

1=Mild, 2=Moderate, 3=Severe, 4=Life-threatening

21) Suspected relationship |_|_|

0=None, 1=Unlikely, 2=Possible, 3=Probable, 4=Definite

22) If the event occurred in association with medication, was the event listed on the medication package insert? |_|_|

1=Yes, 2=No, 3=N/A

Appendix T.WHO Grading for Determining Severity of Adverse Events

Appendix: WHO TOXICITY GRADING SCALE FOR DETERMINING THE SEVERITY OF ADVERSE EVENTS
WHO Toxicity Grading Scale for Determining The Severity of Adverse Events

HEMATOLOGY				
ITEM	Grade 1 Toxicity	Grade 2 Toxicity	Grade 3 Toxicity	Grade 4 Toxicity
Hemoglobin	9.5 - 10.5 gm/Dl	8.0 - 9.4 gm/Dl	6.5 - 7.9 gm/Dl	< 6.5 gm/Dl
Absolute Neutrophil Count	1000-1500/mm ³	750-999/mm ³	500-749/mm ³	<500/mm ³
Platelets	75000-99000/mm ³	50000-74999/mm ³	20000-49000/mm ³	<20000/mm ³
Prothrombin Time (PT)	1.01 - 1.25 x ULN	1.26-1.5 x ULN	1.51 -3.0 x ULN	>3 x ULN
Activated Partial Thromboplastin (APPT)	1.01 -1.66 x ULN	1.67 - 2.33 x ULN	2.34 - 3 x ULN	> 3 x ULN
Fibrinogen	0.75 - 0.99 X LLN	0.50 - 0.74 x LLN	0.25 - 0.49 x LLN	< 0.25 x LLN
Fibrin Split Product	20-40 mcg/ml	41-50 mcg/ml	51-60 mcg/ml	> 60 mcg/ml
Methemoglobin	5 - 9.9 %	10.0 - 14.9 %	15.0 - 19.9%	> 20 %
LIVER ENZYMES				
AST (SGOT)	1.25 - 2.5 x ULN	2.6 - 5 x ULN	5.1 - 10 x ULN	> 10 x ULN
ALT (SGPT)	1.25 - 2.5 x ULN	2.6 - 5 x ULN	5.1 - 10 x ULN	> 10 x ULN
GGT	1.25 -2.5 x ULN	1.6 - 5 x ULN	5.1 - 10 x ULN	> 10 x ULN
Alkaline Phosphatase	1.25 - 2.5 x ULN	1.6 - 5 x ULN	5.1 - 10 x ULN	> 10 x ULN
Amylase	1.1 - 1.5 x ULN	1.6 - 2.0 x ULN	2.1 - 5.0 x ULN	> 5.1 x ULN
CHEMISTRIES				
Hyponatremia	130-135 mEq/L	123-129 mEq/L	116-122 mEq/L	< 116 or mental status changes or seizures
Hypernatremia	146-150 mEq/L	151-157 mEq/L	158-165 mEq/L	> 165 mEq/L or mental status changes or seizures
Hypokalemia	3.0 - 3.4 mEq/L	2.5 - 2.9 mEq/L	2.0 - 2.4 mEq/L or intensive replacement Rx required or hospitalization required.	< 2.0 mEq/L or paresis or ileus or life-threatening arrhythmia
Hyperkalemia	5.6 - 6.0 mEq/L	6.1 - 6.5 mEq/L	6.6 - 7.0 mEq/l	> 7.0 mEq/L or life-threatening arrhythmia
Hypoglycemia	55-64 mg/dL	40-54 mg/dL	30-39 mg/dL	<30 mg/dL or mental status changes or coma

Appendix: WHO TOXICITY GRADING SCALE FOR DETERMINING THE SEVERITY OF ADVERSE EVENTS

CHEMISTRIES (continued)				
Hyperglycemia (note if fasting)	116 - 160 mg/dL	161- 250 mg/dL	251 - 500 mg/dL	> 500 mg/dL or ketoacidosis or seizures
Hypocalcemia (corrected for albumin)	8.4 - 7.8 mg/dL	7.7 - 7.0 mg/dL	6.9 - 6.1 mg/dL	< 6.1 mg/dL or life threatening arrhythmia or tetany
Hypercalcemia (correct for albumin)	10.6 - 11.5 mg/dL	11.6 - 12.5 mg/dL	12.6 - 13.5 mg/dL	> 13.5 mg/dL life-threatening arrhythmia
Hypomagnesemia	1.4 - 1.2 mEq/L	1.1 - 0.9 mEq/L	0.8 - 0.6 mEq/L	< 0.6 mEq/L or life-threatening arrhythmia
Hypophosphatemia	2.0 - 2.4 mg/dL	1.5 -1.9 mg/dL or replacement Rx required	1.0 -1.4 mg/dL intensive Rx or hospitalization required	< 1.0 mg/dL or life-threatening arrhythmia
Hyperbilirubinemia	1.1 - 1.5 x ULN	1.6 - 2.5 x ULN	2.6 - 5 x ULN	> 5 x ULN
BUN	1.25 - 2.5 x ULN	2.6 - 5 x ULN	5.1 - 10 x ULN	> 10 x ULN
Creatinine	1.1 x 1.5 x ULN	1.6 - 3.0 x ULN	3.1 - 6 x ULN	> 6 x ULN or required dialysis
URINALYSIS				
Proteinuria	1+ or < 0.3% or <3g/L or 200 mg - 1 gm loss/day	2 -3 + or 0.3 - 1.0% or 3-10 g/L 1- 2 gm loss/day	4+ or > 1.0% or > 10 g/L 2-3.5 gm loss/day	nephrotic syndrome or > 3.5 gm loss/day
Hematuria	microscopic only	gross, no clots	gross+ clots	obstructive or required transfusion
CARDIAC DYSFUNCTION				
Cardiac Rhythm		asymptomatic, transient signs, no Rx required	recurrent/persistent; No Rx required	requires treatment
Hypertension	transient inc. > 20 mm; no Rx	recurrent, chronic, > 20 mm, Rx required	requires acute Rx; No hospitalization	requires hospitalization
Hypotension	transient orthostatic hypotension, No Rx	symptoms correctable with oral fluids Rx	requires IV fluids; no hospitalization required	requires hospitalization
Pericarditis	minimal effusion	mild/moderate asymptomatic effusion, no Rx	symptomatic effusion; pain; EKG changes	tamponade; pericardiocentesis or surgery required
Hemorrhage, Blood Loss	microscopic/occult	mild, no transfusion	gross blood loss; 1-2 units transfused	massive blood loss; > 3 units transfused

Appendix V. Qualitative questionnaires for the Acceptability Assessment – Individual Interviews with Refusers

Barcode: _____

Auto populate this field as this questionnaire will be triggered by individual refusing to participate in RACD/TPE individual level questionnaire. Grey-out (disable) so Agent cannot make changes.

Capture GPS Coordinates: Latitude (_____) Longitude (_____)

Distance from index case: _____

Auto populate this field, after Surveillance Agent captures GPS coordinates, tablet should calculate distance from index case by comparing with GPS coordinates of index case

Study arm (select one): RACD TPE

Participant age: _____

Auto-populate based on information collected from household level questionnaire

Participant gender: _____

Auto-populate based on information collected from household level questionnaire

Participant occupation (drop down list)

- | | | |
|--|---|--|
|  Student |  Child or minor but not a student |  Unemployed |
|  Farming/Agriculture |  Manufacturing/Factory |  Other Manual Labor |
|  Small-market sales or trade |  Office or Clerical Work |  Other (specify _____) |

Surveillance Agent Name, check all that apply

- [name] [name] [name] [name] [name] [name] [name]
 [name] [name] [name] [name] [name] Other _____

Thank you for answering a few questions for us. These questions will take approximately 5-10 minutes to answer. Your information will help us design interventions that are best for the community in future work to eliminate malaria.

- Do you mind telling me what your concerns are about participating in this intervention?

- Have you ever been part of a malaria screening before? Yes No
 - If yes, when? _____ (*calendar pop up*)
- Have you ever refused to take part in a malaria screening in the past? Yes No
 - If yes, why did you refuse? _____
- If you have been part of a malaria screening in the past (before this study), did you test positive for malaria? Yes No
 - If yes, did you take medication? Yes No
- Has anything in the past with medication influenced your decision not to participate in the intervention? Yes No
 - If yes, what was the problem? _____
- Have you previously had malaria? Yes No
- If yes, when was the last time you had malaria? _____ yrs _____ months _____ days
- Were you informed about the intervention before the malaria nurses visited your household? Yes No
 - If yes, how did that information influence your decision to refuse?

-
- If you were not informed earlier, how did the information you received on the day of the intervention influence your decision to refuse?

-
- Is there anything that would make you decide differently in the future?

-
- What do you think is the best way to get rid of malaria in Swaziland?
-

Appendix W. – Qualitative questionnaires for the Acceptability Assessment – Focus Groups with TPE Participants

Semi-structured interview guide

Focus Group ID # _____

Number of participants: _____

Total number of women: _____

Total number of men: _____

Participant age range: _____

List of participant occupations: _____

Previous participant in this clinical trial? YES NO

Date of interview _____

Start time _____ End time _____

Initials of interviewer _____

Signed informed consent:

These questions are loosely structured and meant to explore why community members choose to opt in or out of the clinical trial. The focus group discussion is intended to be 60 minutes. The researcher leading the focus group will describe the session, what topics will be discussed, expectations of member participation, and explain informed consent. Each participant will have to sign an individual informed consent that includes demographic information on a separate document. The demographic information and names will not be made public and are for the purpose of ensuring diversity in the focus group.

I. Background and experience with malaria, perception of risk in the community

- How many of you have lived in this community for at least 5 years? If you have not, where else have you lived?
- How many of you have had malaria in the last 5 years?
- Has the number of times you have had malaria changed in those 5 years? If yes, how?
- If you have had malaria, were you tested? If not, why not?
- If you were tested and the test was negative, did you take medication?
- What about medication for malaria? Tell me about your experiences taking medication for malaria. What kinds, what happened, where did you obtain it?
- Do you know other people who have had malaria, other than the index case in this screening study? If yes, what is your relationship to them?
- Do you think you are at risk for malaria? Why or why not?
- Who do you think is at risk for malaria? What should they do to protect themselves?
- Do you sleep under a bed net? Why or why not? Tell me more about how you feel about a bed net. Do you think it works? What are some of the problems, if any, you have experienced with your bed net?
- What else do you do to prevent malaria?

II. What experiences will most influence community uptake of the intervention?

These questions refer to any experiences in the past with malaria screening, NOT the focus group members experience during this clinical trial

- Have you ever been part of the NMCPs screening for malaria in affected communities? (If no, STOP, ask whether they have refused in the past or not had the opportunity to be part of a screening and then go to questions about experience during this clinical trial) If YES, continue with other questions.
- When did you participate in screening? How was your experience with the screening test done by the NMCP officers?
- Did you know when you were tested that an index case (your family member or neighbor) was suffering from malaria? If yes, do you know if the index case was a family member or neighbor?
- How far from the index case did you live? What do you think were the reasons your family member or neighbor (index case) got malaria?
- Do you think you were at risk since someone living near you got malaria? How about the risk for your family members?
- Are there people in your household you believe are at greater risk for malaria? Why or why not?
- If you have been part of a malaria screening in the past (before this study), did you test positive for malaria? Did you believe the test results? Why or why not?
- Are you aware of people in your area who have been screened or tested for malaria before? Please share their experiences with me if they did inform you.

*These questions refer to your experience during **this** clinical trial:

- Tell me about this malaria screening. How were you contacted? Who did you speak to and what was the message they gave you?
- What or who made you decide to participate? Tell me about your decision to be part of the screening.
- Are there other times or circumstances when you might decide not to accept medication if you have not been tested for malaria first?
- Do you feel differently or make different decisions about giving medication to your children? How?
- How did you learn about this intervention? Tell me what you thought when you first heard of it.
- Tell me about the time of day when you were contacted about the intervention, if you were home or work or elsewhere? Were you with family members? How far from the index case do you live?
- Why do you think your family member or neighbor (index case) got malaria? Do you think you are at risk since someone living near you got malaria? How about anyone in your family?
- Are there people in your village who you believe are at greater risk for malaria? Why or why not?
- Is this the first time you took malaria medication without being tested first? Would you do it again?
- What do you think about getting tested for malaria before you take medication? Is it important? Why or why not? Do you always get a malaria test when you have a fever? Why or why not? What do you do when the test is negative?
- Would you encourage others in your area to accept treatment before the start of the malaria season as prevention for malaria?

III. Impact of the intervention on daily life

- Have you ever taken malaria medication before?
- If yes, how did malaria medication make you feel after taking it? Were there any uncomfortable side effects? If yes, what were they?
- How about any other medications for malaria? If yes, how was it the same or different from this one?
- Would you take this medication again? Why or why not?
- Did you finish your medication? Why or why not?
- If medication was not finished, please explain why you didn't finish your medication.
- Do you think you can have malaria but not have symptoms?
- Do you think people should be tested before they take malaria medication? Why or why not?
- Do you believe giving malaria medication to everyone living near someone who has tested positive for malaria is a good way to get rid of malaria in Swaziland? Why or why not?

FOR ALL PARTICIPANTS IN THE QUAL STUDY:

- Do you have any other suggestions on how the NMCP can keep you informed and protected from malaria?
- What do you think is the best way to completely eliminate malaria in Swaziland?

Appendix X. Qualitative questionnaires for the Acceptability Assessment – Focus Groups with Malaria Surveillance Team (RACD & TPE Arms)

Semi-structured interview guide

Study participant ID # _____

Participant age: _____

Participant sex: _____

Date of interview _____

Start time _____ End time _____

Initials of interviewer _____

Signed informed consent:

- What is your overall opinion of this study?
- Do you feel that one of these interventions may be better than the other? If yes, how? If not, why not?
- How does offering TPE affect your job? Is it more or less difficult to implement than RACD? Describe how one intervention differs from the other in terms of implementation
- What do you think is working well? Please elaborate.
- What should be changed in terms of offering the interventions? Please elaborate.
- What do you think should be scaled up? Why?
- What do you think should be scaled back? Why?
- What sort of barriers did you encounter during your involvement with the study? Please describe them, particularly with whom you encountered barriers. (after 1st FGD, ask if this has changed over time and if so, how)
- Were there any particular groups who did not want to participate? Who and why?
- Why do you think those barriers were present?
- How do you think those barriers could be addressed?
- Did you do anything to overcome those barriers? If yes, what did you do?
- Were there any particular groups that were receptive to the interventions? Who and why? (after 1st FGD, ask if this has changed over time and if so, how)
- What effect do you think this study is having the community? Please elaborate. Do you notice a change in the effect over time?
- Do you think the community members you encounter understand this study and why it is being done?
- What do you think will define success in this trial?
- Is there anything else you would like to add?

